7.2.2 National Institutes of Health Stroke Scale

The NIHSS is a standardized neurological examination score, with scores ranging from 0 to 42, with higher scores indicating increasing severity. The scale includes measures of level of consciousness, extra ocular movements, motor and sensory tests, coordination, language and speech evaluations. The NIHSS will be administered at Baseline, Post-EVT (2 Hours), 24 and 48 Hours, Day 5 or discharge, and Days 30 and 90.

The NIHSS scores will be dichotomized into 0-2 (indicating a good neurological outcome) versus >2 (indicating otherwise). The proportion of subjects achieving a good neurological outcome at Day 90 or the last rating in NA-1 versus placebo control subjects will be compared using the same logistic regression model as in the primary efficacy analysis. Results will be summarized and tabulated.

7.2.3 Barthel Index

The BI is an index of functional independence with scores ranging from 0 to 100, with higher scores indicating greater independence in activities of daily living and mobility. The BI will be scored at Baseline (pre-morbid) and on Days 30 and 90. Note that the original Barthel Index was a scale from 0-20, but this study will use the modified version. The modified Barthel index simply multiplies the original scale by 5.

The BI scores will be dichotomized at 0-90 (indicating otherwise) versus 95-100 (indicating independent functioning with activities of daily living). The proportion of subjects with independent functioning with activities of daily living at Day 90 in NA-1 versus placebo control subjects will be compared using the same logistic regression model as in the primary efficacy analysis. Results will be summarized and tabulated.

7.2.4 Mortality

Mortality will be assessed at Day 5 or discharge and at Days 30 and 90. Mortality rates, defined as the number of deaths observed divided by the number of subjects observed over the 90-day study period between NA-1 and placebo control subjects, will be analyzed by the same logistic regression model as in the primary efficacy. Subjects with missing outcomes will be treated as deaths for this analysis. The odds ratio associated with the treatment effect, adjusted for the stratification and covariates as described for the primary endpoint analysis, will be presented with a 95% confidence interval and the associated Wald test.

7.2.5 Proportion of subjects with Day 90 mRS ≤ 1

The Day 90 mRS score will be dichotomized at $mRS \leq 1$ (indicating freedom from disability) vs. $mRS > 1$ (indicating otherwise). The proportion of subjects with freedom from dependence/disability based on this dichotomy on Day 90 in NA-1 versus placebo control subjects will be compared using the same logistic regression model as in the primary efficacy analysis. Results will be summarized and tabulated.

7.3 Tertiary Efficacy Outcomes Analyses

Summary statistics for each tertiary efficacy endpoint will be tabulated by treatment group. The tertiary analyses will be considered exploratory. The tertiary efficacy endpoints include the:

- Health-related quality of life, as measured by the EQ-5D-5L at Day 90 or the last rating.
- Volume of acute stroke as measured by a) DWI and b) FLAIR at 24 Hour follow-up. If NCCT was done instead of MRI, Volume of stroke will be derived from hypodense areas.

- Cognitive outcomes, as measured by the 15-item Boston Naming Test (BNT15), Sunnybrook Hemispatial Neglect Procedure (SNAP) and the Montreal Cognitive Assessment (MoCA).
- The proportion of subjects experiencing a favorable functional outcome 30 days post-randomization, defined as 0 to 2 on the mRS.

7.3.1 EQ-5D-5L

The EQ-5D-5L is a generic instrument for describing and valuing health. It is based on a descriptive system that defines health in terms of five dimensions: Mobility, Self-Care, Usual Activities, Pain/Discomfort, and Anxiety/Depression. Each dimension has five response categories corresponding to no problems, slight, moderate, severe and extreme problems. The instrument is designed for self-completion, and respondents rate their overall health on the day of the interview on a 0-100 hash-marked, vertical visual analogue scale (EQ-VAS). The EQ-5D-5L will be completed at Day 30 and Day 90.

For the EQ-5D-5L, the difference between NA-1 and placebo control subjects in the distribution of the EQ-VAS score at Day 90 will be summarized descriptively and modeled as a continuous variable. An analysis of covariance (ANCOVA) model will be fit to the EQ-VAS endpoint with the NA-1/placebo treatment indicator variable and the 7 stratification variables and covariates used in the primary and secondary efficacy analyses. ANCOVA results will be summarized in a table.

7.3.2 Volume of Stroke

All subjects will undergo a follow-up brain MRI [including a minimum of axial DWI, gradient-echo (GRE), FLAIR] at 24 ± 12 hours from the time of randomization. The 24-hour MR is considered a standard of care imaging procedure; if MR is unavailable, then NCCT is allowed. The 24 hour MR (and where MR is unavailable, CT) will be used to assess 24 Hour infarct volume. Infarct volume determinations will not be conducted until after database lock.

The total volume of new a) DWI and b) FLAIR lesions in NA-1 versus placebo control subjects will be calculated from the 24-hour imaging. Where MR is not available, infarct volumes will be determined from the 24-hour CT scan. The plan for combining CT and MRI data will be detailed in the imaging adjudication charter. Total volume

will be assessed using a linear regression using a cubic root transformation if needed. An ANCOVA will be fit and summarized as per the EQ-VAS model.

7.3.3 Cognitive Outcomes

These will be explored using the BNT15, SNAP and the MoCA scores. The BNT15 is a widely used neuropsychological assessment tool to measure confrontational word retrieval in individuals with aphasia or other language disturbance caused by various neurological disorders. The SNAP is a short bedside battery for visuoconstructive hemispatial neglect. The MoCA has been found to be a feasible global cognitive screening tool in stroke trials.

The BNT15 (short form), SNAP and MoCA will be administered at Day 90. Assessments will only be conducted if the tool/scale is available in the local country language. If the assessment is not conducted for language reasons the outcome will not be measured for those subjects.

BNT15 (scale=0-15) and SNAP total scores (scale=0-100) will be analyzed and summarized as continuous endpoints using the basic ANCOVA models described in the two previous sections. As is standard practice, the MoCA scores (0-30) will be dichotomized at 26 and analyzed in the same type of logistic regression model as has been described for the primary endpoint. MoCA scores ≥ 26 are considered to indicate normal cognition (Nasreddine, 2005, Smith, 2007).^[15, 16] Results will be summarized and tabulated as in the primary efficacy analysis.

7.3.4 mRS at 30 Days

The proportion of subjects experiencing a favorable functional outcome 30 days post-randomization, defined as 0 to 2 on the mRS, will be analyzed in the same type of logistic regression model as the primary endpoint. Results will be summarized and tabulated as in the primary efficacy analysis.

7.4 Exploratory Analyses

In addition to the primary and secondary analyses adjusting for age, sex, baseline NIHSS score, baseline ASPECTS, intravenous alteplase, declared first device, occlusion location and site, exploratory subgroup analyses will be conducted to

determine whether any of these factors can modify the effect of the NA-1 vs. placebo treatments. Sub-group analyses will be performed on the primary outcome and include forest plots to display effect sizes by sub-group⁶.

Dichotomous sub-groups of interest include the following:

1. Age > 80 years of age
2. Sex (men vs. women)
3. Treatment with intravenous alteplase (yes/no)
4. Treatment by first declared thrombectomy device (Stent vs. Aspiration)
5. Subjects whose time from onset of stroke symptoms to NA-1 (or placebo) treatment was ≤ 6 hrs vs. > 6 hours.
6. Severe stroke defined as NIHSS > 20 vs. NIHSS ≤ 20 .
7. Outcomes by recognized ethnic and racial groups.
8. Outcomes by degree of reperfusion (TICI $\geq 2b$ vs. TICI $< 2b$)
9. General anesthesia vs. no general anesthesia
10. Baseline occlusion location (MCA vs. ICA)
11. Subjects whose time from onset of stroke symptoms to NA-1 (or placebo) treatment was ≤ 4 hrs vs. > 4 hours.
12. Subjects weighing between 105-120 kg.
13. ASPECTS score of 5-7 vs. 8-10

Additional sub-groups may be examined, but those specified above are of prior clinical interest.

Effect sizes will be estimated as subgroup-specific odds ratios ($\pm 95\%$ CIs) as follows. Separate logistic regression models for the primary endpoint, with treatment group and the stratification variables and covariates used in the minimization algorithm as predictors, will be fit to each of the subject subgroups (e.g., a model will be fit to males

and a second model will be fit to females). The estimated (NA-1/placebo) odds ratios, with 95% confidence intervals will be the NA-1 effect size estimates for each of the subgroups (e.g., for males and for females) and will be displayed in the forest plots.

An additional exploratory analysis will consider the time from administration of tPA to infusion start and its effect on the primary efficacy outcome. This will be assessed by performing the logistic regression for the primary efficacy outcome, with an additional term added for the time interval between tPA administration and start time of infusion. This time may be positive or negative, depending on whether tPA administration or infusion occurred first, although it is expected that most subjects will receive tPA before drug infusion. The time should be calculated as “start time of drug infusion” minus “time of tPA administration”.

In addition to the subgroup analyses described above, the analyses of the primary and secondary endpoints will be repeated with additional terms for period (e.g., before/after 100-subject IDMC; before/after 300-subject IDMC; before/after 600-subject IDMC) and period by treatment interaction. Simple effects within period and the interaction of treatment with period will be viewed to assess the homogeneity of the study data across periods before and after the various IDMC meetings. Also, the percentage of patients with functional independence at 90 days as defined by a 90 day mRS of 0-2 will be plotted against the time from stroke symptom onset to the time of study drug administration for each of NA-1 and placebo.

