11.7 Adjustment for Covariates and Subgroup Analyses

In addition to the primary and secondary analyses adjusting for age, sex, baseline NIHSS score, baseline ASPECTS score, occlusion location, intravenous alteplase use, declared first endovascular device and site, exploratory analyses will be conducted to determine the potential roles of common baseline characteristics and assess potential heterogeneity of treatment effect across subgroups. Specific subgroups of interest include the very elderly (age > 80 years), men vs. women, subject with different baseline stroke severity (on NIHSS and measured radiologically on ASPECTS), subject treated with intravenous alteplase (yes/no), declared first endovascular approach, baseline occlusion location (MCA vs. ICA), and subject with long/short time from onset to treatment. Full details will be specified in detail in the SAP.

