7.0 EFFICACY ANALYSIS

Efficacy analyses are summarized in [Table 2](#).

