Secondary	Day-90 mRS	Ordinal (0-4,5+6)	ITT	mRS cumulative logits modeled as a function of treatment, baseline ASPECTS, occlusion location, age, sex, baseline NIHSS, alteplase*thromb_app, study site
	Day-90 NIHSS	Binary (≤ 2 vs. > 2)	ITT	logit(binary NIHSS) modeled as a function of treatment, baseline ASPECTS, occlusion location, age, sex, baseline NIHSS, alteplase*thromb_app, study site
	Day-90 Barthel	Binary (< 95 vs. ≥ 95)	ITT	logit(binary Barthel Index) modeled as a function of treatment, baseline ASPECTS, occlusion location, age, sex, baseline NIHSS, alteplase*thromb_app, study site
	Day-90 Mortality	Binary day-90 death status	ITT	logit(binary death status) modeled as a function of treatment, baseline ASPECT, occlusion location, age, sex, baseline NIHSS, alteplase*thromb_app, study site
	Day-90 mRS	mRS Binary (≤ 1 vs. > 1)	ITT	logit(binary mRS) modeled as a function of treatment, baseline ASPECTS, occlusion location, age, sex, baseline NIHSS, alteplase*thromb_app, study site
Tertiary	EQ-VAS	0-100	ITT	EQ-VAS modeled as functions of treatment, baseline ASPECTS, occlusion location, age, sex, baseline NIHSS, alteplase*thromb_app, study site
	Stroke volume	continuous	ITT	Stroke volume (or cubic root transformation of stroke volume) modeled as a function of treatment, baseline ASPECTS, occlusion location, age, sex, baseline NIHSS, alteplase*thromb_app, study site
	BNT15	0-15	ITT	BNT15 Score modeled as a function of treatment, baseline ASPECTS, occlusion location, age, sex, baseline NIHSS, alteplase*thromb_app, study site
	SNAP	0-100	ITT	Total SNAP Score modeled as a function of treatment, baseline ASPECTS, occlusion location, age, sex, baseline NIHSS, alteplase*thromb_app, study site
	MoCA	Binary (< 26 vs. ≥ 26)	ITT	logit(binary MoCA) modeled as a function of treatment, baseline ASPECTS, occlusion location, age, sex, baseline NIHSS, alteplase*thromb_app, study site
	Day-30 mRS	Binary (≤ 2 vs. > 2)	ITT	logit(binary mRS) modeled as a function of treatment, baseline ASPECTS, occlusion location, age, sex, baseline NIHSS, alteplase*thromb_app, study site
Exploratory	Day-90 mRS	Binary (≤ 2 vs. > 2)	ITT	Separate logistic regression models in which the logit(binary mRS) is modeled as a function of treatment only, by each of the subgroups to be considered in the Subgroup forest plots

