	Day-90 mRS	Binary (≤ 2 vs. > 2)	ITT	logit(binary mRS) modeled as a function of treatment, baseline ASPECTS, occlusion location, age, sex, baseline NIHSS, alteplase*thromb_app, study site, period, and treatment by period interaction

Statistical Analysis Plan

Endpoint Type	Endpoint	Scale	Population	Statistical Model
	All secondary endpoints	As listed above	ITT	Modeled as described above as a function of treatment, baseline ASPECTS, occlusion location, age, sex, baseline NIHSS, alteplase*thromb_app, study site, period, and treatment by period interaction
	Day-90 mRS	Binary (≤ 2 vs. > 2)	ITT	logit(binary mRS) modeled as a function of treatment, baseline ASPECTS, occlusion location, age, sex, baseline NIHSS, alteplase*thromb_app, study site, and time between tPA administration and infusion start

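### The SAP gives two different models for the same subgroup forest plots, and neither produces the treatment-by-subgroup contrast that the stated aim calls for

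*SAP*

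**What the plan says.** **Aim.** Protocol 11.7 wants to "assess potential heterogeneity of treatment effect across subgroups" and leaves the details to the SAP. SAP 7.4 wants to "determine whether any of these factors can modify the effect of the NA-1 vs. placebo treatments", where the factors are those adjusted for in the primary model.

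**Model in the text.** SAP 7.4 lists 13 subgroups. It fits "Separate logistic regression models for the primary endpoint, with treatment group and the stratification variables and covariates used in the minimization algorithm as predictors", one model per subgroup level, and plots the resulting odds ratios with 95% CIs.

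**Model in the table.** For the same endpoint (Day 90 mRS 0–2), population (ITT) and forest plots, the Exploratory part of SAP Table 2 reads "Separate logistic regression models in which the logit(binary mRS) is modeled as a function of treatment only, by each of the subgroups".

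**Standing of the table.** SAP 7.0 says "Efficacy analyses are summarized in" Table 2. SAP 7.1.3, directly after the adjusted primary model, says that odds ratios will also be tabulated for selected subpopulations.

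**Other relevant plans in SAP 7.4.** An interaction is planned for calendar period: "Simple effects within period and the interaction of treatment with period will be viewed to assess the homogeneity of the study data". Table 2 accordingly ends the predictor list for that model with "study site, period, and treatment by period interaction". The share of patients independent at Day 90 "will be plotted against the time from stroke symptom onset to the time of study drug administration for each of NA-1 and placebo".

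**The concern.** There are two faults.

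First, an adjusted and an unadjusted logistic model estimate different odds ratios. While both stand in the SAP, either set could be presented as prespecified.

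Second, the question is whether the effect differs between levels, but the planned output is a separate estimate for each level. Readers of such a plot tend to compare which intervals cross 1, and that is not a test of difference. The SAP asks for an interaction where it wants one (period), so its absence here looks like a gap rather than a general choice.

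At stake is how the subgroup results are read, not the trial's main conclusion.

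**Working it through.** **1. The two models side by side.** SAP 7.4: treatment, stratification variables and minimization covariates. Table 2: treatment alone. The other logistic rows of Table 2 list their covariates in full, so the row is a different model and not an abbreviation.

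**2. Which subgroups the aim covers.** Of the 13 items, seven are adjustment factors: age (1), sex (2), alteplase (3), declared device (4), NIHSS (6), occlusion location (10) and ASPECTS (13). Protocol 11.7 adds onset-to-treatment time, which SAP 7.4 cuts twice: at 6 hours (5) and at 4 hours (11). The other four items (7, 8, 9, 12) are neither adjustment factors nor named in protocol 11.7.

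**3. Anchor to the plan's own figure.** Inputs from SAP 1.4: 52% versus 60.7%; 1076 evaluable, read as 538 per arm; two-sided 0.05.
- SE of the difference = √[(0.52×0.48 + 0.607×0.393)/538] = 0.0301.
- Fixed-design power = Φ(0.087/0.0301 − 1.96) ≈ 82.3%.
- With one O'Brien-Fleming-type look at 600/1076 = 55.8%, power is 82.1% (stated: 81.7%). One-sided boundaries are 0.0027 and 0.0241 (stated in SAP 3.0: 0.003 and 0.024). The inputs reproduce the plan.

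**4. How far apart the two models are.** Unadjusted OR = (0.607/0.393)/(0.52/0.48) = 1.43. The adjusted OR giving the same two proportions, averaged over a normal prognostic score, is 1.46, 1.53 or 1.65 for an assumed score SD of 0.5, 1.0 or 1.5. That is 2%, 8% or 16% higher. For comparison, SE(log OR) = √[1/(538×0.2496) + 1/(538×0.2386)] = 0.1234, so a half-sample subgroup CI is the OR times or divided by exp(1.96×0.1234/√0.5) = 1.41.

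**5. What per-level intervals show when the effect is uniform.** With level powers a and b, the chance that exactly one interval excludes 1 is a(1−b) + b(1−a). Unadjusted design values, assumed splits:

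| Split | a, b | Chance |
|---|---|---|
| 50/50 | 0.530, 0.530 | 50% |
| 25/75 | 0.300, 0.703 | 58% |
| 10/90 | 0.146, 0.780 | 70% |

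A properly fitted interaction test errs nominally 5% of the time.

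**6. Precision of the missing contrast.** For the adjusted full-ITT model, simulation (1076 subjects, prognostic SD 1.0, 15 to 60 site levels, all assumed beyond the sample size) gives the SE of the log ratio of ORs. The ratio detectable with 80% power is exp(2.80×SE), and the 95% CI factor is exp(1.96×SE).

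| Split | SE | Detectable ratio | CI factor |
|---|---|---|---|
| 50/50 | 0.28–0.29 | 2.2–2.3 | 1.73–1.77 |
| 70/30 | 0.30–0.32 | 2.3–2.45 | 1.80–1.87 |
| 80/20 | 0.35–0.37 | 2.7–2.8 | 1.99–2.07 |

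The unadjusted shortcut 0.1234/√[f(1−f)] gives 0.247, 0.269 and 0.309, hence 2.00, 2.13 and 2.37. Those figures belong to the treatment-only model and overstate the precision of the adjusted one.

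**7. Site terms fitted within each level.** SAP 6.5 pools sites to at least 5 randomized subjects across the trial, not within a subgroup level. Simulated median ORs in the smaller level (true adjusted OR 1.53; ranges span different assumed site-size patterns):

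| Level share | Site levels | Per-level model | Single model |
|---|---|---|---|
| 10% | 60 | 2.27–2.53 | 1.57–1.66 |
| 10% | 30 | 1.79–2.13 | 1.51–1.64 |
| 20% | 60 | 1.78–1.85 | 1.59–1.61 |
| 20% | 30 | 1.55–1.72 | 1.51–1.57 |
| 20% | 15 | 1.61 | 1.54 |
| 50% | 30–60 | 1.58–1.62 | 1.55–1.58 |

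A contrast formed by hand from two per-level fits was falsely significant in 10–13% of trials for a 10% level with 30–60 sites, against 5–6% for the interaction term. For a 20% level with 15 sites the rates were 5.8% and 4.5%.

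**8. Multiplicity.** Chance of at least one false-positive interaction if independent: 1 − 0.95⁷ = 30% for the seven factors, and 1 − 0.95⁹ = 37% with both onset-time cuts. Those two cuts overlap, so the second figure is somewhat high.

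**The case against.** The strongest reply is that little hangs on this. The analyses are exploratory and outside the fixed testing sequence. Two places in the body of the SAP (7.1.3 and 7.4) lean toward the adjusted model, and 7.0 calls Table 2 a summary, so the row is probably a one-line error. The scale difference is small beside subgroup intervals. The plots show confidence intervals, from which a reader could derive a ratio of odds ratios, and onset time also has a by-arm plot. The proposed contrast has low power.

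Most of this stands and limits the weight of the point. It does not remove it. A probable slip still needs correcting when no precedence is stated. A plot by arm for one factor is not a contrast for eight. A contrast left to readers is not prespecified, and in small levels with many sites it is also less reliable.

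A reader might infer that fitting the model within each level generally biases the subgroup odds ratios. The documents do not support that: they give neither the number of sites nor the subgroup shares, and step 7 shows little effect at an even split and modest effects at 20% with fewer sites.

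**Conclusion.** The point holds on the text. SAP 7.4 and Table 2 conflict on the model for the same forest plots, with Table 2 the likely outlier. Neither supplies a treatment-by-subgroup contrast for the aims in SAP 7.4 and protocol 11.7.

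The consequence is limited to exploratory output. A reader might infer that the primary analysis or error control is compromised; neither uses these models. Nor would adding interactions settle whether the effect is uniform. At the precision in step 6, the 95% CI of a ratio of ORs is about times or divided by 1.7 to 2.1, so a non-significant result is not evidence of uniformity.

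Confidence is high for the textual conflict and the missing contrast. It is lower for the simulated sizes, which rest on assumed prognostic strength, site numbers and subgroup shares. Material inflation from per-level site terms is confined to levels of roughly 10–20% of subjects with many sites.

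**What to change.** Before unblinding:

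1. Correct the Table 2 row so that it and SAP 7.4 state one adjusted model.
2. For each of the seven adjustment factors with a listed subgroup, and for onset-to-treatment time at both cut-points (items 5 and 11), fit one model in the full ITT population: the primary-model covariates plus subgroup and treatment-by-subgroup. Report the subgroup ORs and the ratio of ORs with its 95% CI from that model.
3. Label the results exploratory, without multiplicity control and with low power, and state that a non-significant interaction does not show a uniform effect.

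The cost is SAP wording and one interaction term per contrast, plus the subgroup indicator where the primary model does not already contain it. No new data are needed. There are two downsides: a few more exploratory p-values if these are shown, and the single model's assumption that covariate and site effects are common to both subgroup levels, which the SAP should state.

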9.8 Pharmacokinetics Assessment

Actual sampling time-points will be recorded and used for PK calculations. If data permit, the following PK parameters for NA-1 will be calculated at the end of the study by standard noncompartmental methods for all subjects with PK samples:

- **AUC_{0-t}**: Area under the concentration-time curve from time zero to time of last measurable concentration
- **AUC_{0-inf}**: Area under the concentration-time curve from time zero to infinity
- **C_{max}**: Maximum plasma concentration observed after dosing
- **T_{max}**: Time to occurrence of C_{max}
- **t_{1/2}**: Terminal elimination half-life

Samples with no detectable NA-1 will be excluded from analysis (placebo). A further analysis of the effect of administration of thrombolytic therapy (alteplase) on the pharmacokinetics of NA-1 will also be performed.

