1.3 Study Design

This is a Phase 3 randomized, multicenter, blinded, placebo-controlled, parallel group, single-dose design. Per inclusion/exclusion criteria, subjects suffering an acute stroke who are selected for endovascular revascularization in accordance with local institutional practices and who present with a small established infarct core with good collateral circulation, will be given a single, 2.6 mg/kg (up to a maximum of 270 mg) intravenous dose of NA-1 or placebo. Ideally, dosing should begin within 30 minutes of randomization and within 60 minutes of the NCCT.

A total of 1120 subjects aged 18 years and older will be enrolled into the study. A patient who consents but is not randomized will be considered a screen failure. A subject is considered randomized the moment the randomization process is completed on-line. This is time “0” for the study. All subjects will be followed for 90 days (or until death if prior to 90 days). Subjects who are randomized but do not receive study drug will still be followed through the 90-day study period. The end of study is defined as the date that the last enrolled subject has completed their Day 90 visit.

The Schedule of Assessments is presented in [Table 1](#).

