1.5 Randomization

Treatments (placebo vs. NA-1) will be assigned 1:1 by application of a stratified minimization algorithm administered through a secure web-based, real-time interaction with the site and the central server. The time of randomization on the central server will be considered baseline (i.e., time zero) for the study. Study drug is intended to be infused within 30 minutes post-randomization and within 60 minutes of the NCCT. Although each vial of NA-1 or placebo will have a unique ID number that will be linked to the randomization code generated by the minimization algorithm, the vials will appear to be identical to those dispensing them and to the subjects. Thus, individuals at the sites will be blinded to the treatment assignments.

In order to balance the treatment assignment among subjects receiving different combinations of adjunct thrombolytic and thrombectomy therapies, randomization will be stratified by (1) intravenous thrombolysis with alteplase (yes/no) and by (2) a subject's initial thrombectomy approach (stent retriever vs. thrombus aspiration device). Planned initial use of any other endovascular device type or intra-arterial medications will constitute an exclusion criterion. Similarly, if intravenous thrombolysis is planned for the subject, use of any intravenous thrombolytic other than alteplase is an exclusion criterion. Thus, there will be 4 randomization strata:

- a. Alteplase+stent retriever
- b. Alteplase+thrombus aspiration device

- c. Stent retriever without Alteplase
- d. Thrombus aspiration device without Alteplase

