2.0 ANALYSIS POPULATIONS

2.1 Intent-to-Treat Population

The primary efficacy analysis will be conducted on the ITT population, defined as all subjects randomized into the trial with grouping by randomized treatment, regardless of treatment actually received. Deceased subjects will be included in the ITT population with a mRS score of 6, NIHSS of 42 and Barthel Index of 0. An ITT analysis will also be conducted for the secondary endpoints, with subjects grouped according to the randomized (intended) treatment.

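### The exploratory alteplase-timing model fits one slope for both arms: it can describe an association with outcome but cannot show whether timing modifies the NA-1 effect, and its analysis set needs naming

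*SAP*

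**What the plan says.** SAP section 7.4 states the aim: "An additional exploratory analysis will consider the time from administration of tPA to infusion start and its effect on the primary efficacy outcome". The method is the primary-outcome logistic regression "with an additional term added for the time interval between tPA administration and start time of infusion". The covariate is defined in these words: "The time should be calculated as “start time of drug infusion” minus “time of tPA administration". It may be positive or negative.

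The matching row at the end of SAP Table 2 gives the population as ITT. It lists treatment and the usual covariates, including the four-level alteplase*thromb_app term, and ends "study site, and time between tPA administration and infusion start". It contains no product of treatment and interval.

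SAP section 2.1 makes the ITT population all randomized subjects: "defined as all subjects randomized into the trial with grouping by randomized treatment, regardless of treatment actually received". Two of the four randomization strata in SAP section 1.5 have no alteplase, for example "Stent retriever without Alteplase". SAP section 1.3 keeps undosed subjects in follow-up: "Subjects who are randomized but do not receive study drug will still be followed through the 90-day study period".

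Neither section 7.4 nor Table 2 says how a subject with no interval is handled. The missing-data rules in SAP section 5.1 cover outcomes only.

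**The concern.** The question most readers will bring to this analysis is whether NA-1 works differently when it is given sooner or later after alteplase. The plan takes some interest in how the two drugs combine. Alteplase yes/no is a subgroup in SAP 7.4, and Protocol 9.8 states: "A further analysis of the effect of administration of thrombolytic therapy (alteplase) on the pharmacokinetics of NA-1 will also be performed". This model is the only planned efficacy analysis that uses the timing.

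A placebo subject also has an infusion start time, so the interval exists in both arms, but under placebo it cannot carry an NA-1 effect. There it reflects prognosis, transfer and the speed of the care pathway. A slope common to both arms mixes that with any change in the NA-1 effect. A pathway association could later be described as an alteplase-timing signal for NA-1, or a real one could be averaged away.

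The second point is smaller. The interval is undefined for subjects without alteplase and for those never dosed, so a reader cannot tell from the ITT label who is in the fit.

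**Working it through.** **Plan's own figures.** The documents give no sample size, effect size or power for this analysis. As a check on the base rates used below, the trial's stated 81.7% power was recomputed from SAP section 1.4 (52% against 60.7%, 1076 evaluable, so 538 per arm). A fixed design gives 82.1%. With one look at 600/1076 = 0.558 and O'Brien-Fleming-type spending, power is 81.8% (pooled variance) to 82.1% (unpooled), with one-sided boundaries 0.0027 and 0.0241. SAP section 3.0 states 0.003 and 0.024. These figures reproduce.

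**Who has an interval.** The documents give no alteplase share, so a range is assumed. Of 1120 enrolled:

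| Assumed alteplase share | Interval defined (at most) | Undefined (at least) |
|---|---|---|
| 40% | 448 | 672 |
| 60% | 672 | 448 |
| 80% | 896 | 224 |

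Undosed subjects lower the middle column a little further.

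**What one slope estimates.** Let b_P and b_N be the log-odds slopes on the interval under placebo and NA-1. With 1:1 randomization and the same interval distribution in both arms, the common slope is close to (b_P + b_N)/2. Effect modification is b_N − b_P. The average says nothing about the difference.

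**Simulation per hour** (assumed: 800 alteplase-treated subjects, interval mean 1 h and SD 0.5 h, 400 data sets per scenario):

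| b_P, b_N | Common slope, as planned | Treatment-by-interval term, if added |
|---|---|---|
| 0.3, 0.3 (no modification) | 0.30 | −0.03 |
| 0, 0.6 (pure modification) | 0.29 | 0.60 |
| −0.4, 0.4 (opposite slopes) | −0.01 | 0.79 |

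**Simulation per SD of the interval** (N = 1120, 600 data sets per scenario, other covariates omitted). Entries are rejection rates at 40 / 60 / 80% alteplase share:

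| b_P, b_N | Planned slope | Interaction term |
|---|---|---|
| 0, −0.4 | 51 / 68 / 80% | 53 / 72 / 86% |
| −0.2, −0.2 | 54 / 71 / 84% | 4 / 5 / 5% |
| 0.25, −0.25 | 5 / 5 / 5% | 72 / 90 / 96% |

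The planned slope rejects about equally often in the first two rows, although only the first contains effect modification.

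**Precision of the interaction.** These slope differences are large. At SD 0.5 h, 0.4 and 0.5 per SD are 0.8 and 1.0 per hour. A smaller range can be approximated, unadjusted, with response rate p = 0.56 (near the mean of 52% and 60.7%):

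SE(b_N − b_P) = √{2 / [(n/2) · p(1 − p) · SD²]}

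- n = 800: (400)(0.2464)(0.25) = 24.64, so SE = √(2/24.64) = 0.285. Power for 0.3 per hour is Φ(0.3/0.285 − 1.96) = Φ(−0.91), about 18%. For 0.6 it is Φ(0.15), about 56%, which matches the simulated 56%. For 0.8 it is Φ(0.85), about 80%, against 78% simulated.
- n = 448: (224)(0.2464)(0.25) = 13.80, so SE = 0.381. Power is about 12% for 0.3 and 35% for 0.6.

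A difference of 0.6 per hour means that the NA-1 odds ratio changes by a factor of e^0.6 = 1.8 for each hour; 0.8 means a factor of 2.2.

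**Coding of subjects without alteplase.** Giving them a constant interval, with alteplase status kept in the model, left the simulated slope essentially unchanged (at 60% share, −0.201 either way when both slopes are −0.2). The choice does affect the precision of the treatment log-odds ratio in the same model: SE 0.158 with those rows dropped against 0.122 with them kept.

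**The case against.** The strongest reply is that the SAP never claims to test modification here. Its stated aim is the interval's effect on the outcome, and one slope answers that. The next paragraph of SAP 7.4 specifies a period-by-treatment interaction, so the authors wrote interactions where they wanted them. This stands: a reader might infer that the model contradicts its own purpose, and it does not. The gap is in what the result can be used for. Even so, section 7.4 introduces its subgroup analyses as asking which factors modify the NA-1 effect, so an arm-specific term fits the section.

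Several other stronger readings also fail.

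- **That stratifying on alteplase shows the sponsor expects an efficacy interaction.** Protocol 6.2 gives balance between arms as the reason. The pharmacokinetic analysis concerns exposure only.
- **That alteplase as a modifier goes unexamined.** The yes/no subgroup compares the arms with odds ratios and 95% CIs. Only timing is left out.
- **That the ITT label is a breach of the ITT principle.** Table 2 also labels the cognitive scales ITT, although SAP 7.3.3 says they are not collected where no local-language version exists. The label appears to name the source population and the grouping. Software that drops rows with a missing covariate would arrive at nearly the set recommended here.
- **That a zero code would corrupt the slope.** The four-level stratum term carries alteplase status and absorbs a constant.
- **That the placebo arm is ignored.** Placebo subjects and a treatment term are in the model; what is missing is a separate placebo slope.

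It is also fair to say that every slope, the interval spread and the alteplase share used above are assumptions.

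**Conclusion.** The point holds as a limit on interpretation. The planned model can report an association between the alteplase-to-infusion interval and outcome. It cannot separate prognosis or care pathway from a change in the NA-1 effect. That follows from the algebra whatever slopes are assumed; the simulations only illustrate it.

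The set is under-described more than wrong. Between 224 and 672 of 1120 subjects would lack an interval if 80% to 40% receive alteplase, plus any who are never dosed.

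An interaction term would address the right question but would be imprecise. Under the assumed 800 subjects and SD of 0.5 h, power is low unless the slopes differ by about 0.6 log-odds per hour or more. A wider spread of intervals would help, and a lower alteplase share would hurt.

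The analysis is exploratory and outside the fixed testing sequence. No primary or secondary conclusion and no type I error statement depends on it. Severity is minor.

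**What to change.** In SAP 7.4 and the matching row of Table 2:

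- Define the set as ITT subjects with both an alteplase time and a study-drug start time recorded, grouped as randomized. This also settles the undosed subjects, which a restriction to alteplase recipients alone would not.
- Replace alteplase*thromb_app with thromb_app in this model, since alteplase is constant in that set.
- Fit treatment, interval and treatment-by-interval.
- Report the interaction with its 95% CI, the NA-1 odds ratio at a few intervals fixed in advance, and the placebo-arm slope as the prognostic reference.
- State the number of subjects in the fit by arm, and present the result as exploratory.

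The cost is a few lines of SAP text and one model term, with no new data. The downside is a wide interval for the interaction, so a non-significant result must not be read as evidence that timing is irrelevant. Making the change before unblinding avoids choosing the set or the coding after the results are known.
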